### 1.3 Schedule of Activities (SoA)

Study Period	Screening	Active run-in period (5 weeks)		Treatment (12 weeks)			Follow-up (14 days post last dose)	Notes
Visit Number/Title	Visit 1/ Screening	Visit 2	Visit 3	Visit 4/ baseline	Visit 5	Visit 6/ Discontinuation	Phone call	
Scheduled Hour, Day, Week, etc., and Window:	Week -7/-6	Week -5 (±7 days)	Week -1 (+3 days)	Week 0 (±3 days)	Week 6 (±7 days)	Week 12 (±7 days)	±3 days	The dates of Visit 3 and Visit 4 will be decided based on the date of Visit 2, while the dates of Visit 5 & Visit 6 will be decided based on the date of Visit 4.
Administrative Procedures								
Informed Consent	X							
Inclusion/Exclusion Criteria	X			X				
Participant Identification Card	X							The card will be updated once randomized.
Medical History	X							
Prior/Concomitant Medication Review	X	X	X	X	X	X		
Assignment of Screening Number	X							
LDL-C treatment target evaluation based on Cardiac Risk assessment	X							Based on Chinese Guidelines on Prevention and Treatment of Dyslipidemia in Adults (2016 Edition).
Monitor Dietary/Exercise Compliance	X	X	X	X	X	X		
Monitor Medication Compliance			X	X	X	X		
Assignment of Treatment/Randomization number				X				

Study Period	Screening	Active run-in period (5 weeks)		Treatment (12 weeks)			Follow-up (14 days post last dose)	Notes
Visit Number/Title	Visit 1/ Screening	Visit 2	Visit 3	Visit 4/ baseline	Visit 5	Visit 6/ Discontinuation	Phone call	
Scheduled Hour, Day, Week, etc., and Window:	Week -7/-6	Week -5 (±7 days)	Week -1 (+3 days)	Week 0 (±3 days)	Week 6 (±7 days)	Week 12 (±7 days)	±3 days	The dates of Visit 3 and Visit 4 will be decided based on the date of Visit 2, while the dates of Visit 5 & Visit 6 will be decided based on the date of Visit 4.
Run-in atorvastatin administration/dispensing		X						
MK-0653C/ Atorvastatin + matching placebo administration/dispensing				X	X			
Efficacy Procedures								
Lipid Panel A	X		X	X	X	X		LDL-C, total cholesterol (TC), HDL-C, non-HDL-C, and Triglyceride (TG). Blood sample should be drawn after at least 10-hour fasting. Otherwise the visit need to be rescheduled. Result of local lab within 4 weeks prior to Visit 1 can be used as reference for participant screening.
Apo protein (Apo) B				X	X	X		Blood sample should be drawn after at least 10-hour fasting. Otherwise the visit needs to be rescheduled.
Safety Procedures								
Full Physical Examination including height and weight	X			X		X		

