Study Period	Screening	Active run-in period (5 weeks)		Treatment (12 weeks)			Follow-up (14 days post last dose)	Notes
Visit Number/Title	Visit 1/ Screening	Visit 2	Visit 3	Visit 4/ baseline	Visit 5	Visit 6/ Discontinuation	Phone call	
Scheduled Hour, Day, Week, etc., and Window:	Week -7/-6	Week -5 (±7 days)	Week -1 (+3 days)	Week 0 (±3 days)	Week 6 (±7 days)	Week 12 (±7 days)	±3 days	The dates of Visit 3 and Visit 4 will be decided based on the date of Visit 2, while the dates of Visit 5 & Visit 6 will be decided based on the date of Visit 4.
Vital Signs (heart rate, blood pressure)	X	X	X	X	X	X		
12-lead ECG	X							ECG will performed locally and results should be checked and confirmed by the investigator or qualified designee.
Urine/ Serum β-Human Chorionic Gonadotropin (β-hCG; WOCBP only)	X			X	X	X		Serum β-hCG test is determined by central lab if urine pregnancy performed at the site is positive.
fT4 and TSH	X							Result of local lab within 4 weeks prior to Visit 1 can be used as reference for participant screening.
Hematology	X			X		X		Result of local lab within 4 weeks prior to Visit 1 can be used as reference for participant screening.
Urinalysis	X			X		X		Result of local lab within 4 weeks prior to Visit 1 can be used as reference for participant screening.

Study Period	Screening	Active run-in period (5 weeks)		Treatment (12 weeks)			Follow-up (14 days post last dose)	Notes
Visit Number/Title	Visit 1/ Screening	Visit 2	Visit 3	Visit 4/ baseline	Visit 5	Visit 6/ Discontinuation	Phone call	
Scheduled Hour, Day, Week, etc., and Window:	Week -7/-6	Week -5 (±7 days)	Week -1 (+3 days)	Week 0 (±3 days)	Week 6 (±7 days)	Week 12 (±7 days)	±3 days	The dates of Visit 3 and Visit 4 will be decided based on the date of Visit 2, while the dates of Visit 5 & Visit 6 will be decided based on the date of Visit 4.
Chemistry	X		X	X	X	X		Blood sample should be drawn after at least 10-hour fasting. Otherwise the visit need to be rescheduled. Result of local lab within 4 weeks prior to Visit 1 can be used as reference for participant screening.
AE/SAE Monitoring	X	X-----X						The serious adverse events occurred within 14 days after last study drug administration must be reported to Sponsor.

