12. Participant has hypersensitivity or intolerance to ezetimibe, atorvastatin, the ezetimibe/atorvastatin combination tablet, or any component of these medications or has a condition or situation, which described as contraindication in labeling of EZETROL® or Lipitor® or may interfere with participation in the trial in the opinion of the investigator.
13. Participant has disorders of the hematologic, digestive, or central nervous systems including cerebrovascular disease and degenerative disease that in the opinion of the investigator would limit evaluation or participation.
14. Participant has a history of mental instability, drug/alcohol abuse within the past 5 years, or major psychiatric illness not adequately controlled and stable on pharmacotherapy in the investigator's judgement.
15. Participant has a history of myopathy or rhabdomyolysis with ezetimibe or any statin.
16. Participant has a medical condition or personal circumstance which, in the opinion of the investigator, places the participant at unnecessary risk through continued participation in the trial or does not allow the participant to adhere to the requirements of the protocol.

17. A WOCBP who has a positive urine pregnancy test within 24 hours before the first dose of study intervention. If the urine test is positive or cannot be confirmed as negative, a serum pregnancy test will be required.

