## **6 STUDY INTERVENTION**

Study intervention is defined as any investigational intervention(s), marketed product(s), placebo, or medical device(s) intended to be administered to a study participant according to the study protocol.

Clinical supplies [study intervention(s) provided by the Sponsor] will be packaged to support enrollment . Clinical supplies will be affixed with a clinical label in accordance with regulatory requirements.

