### **6.1 Study Intervention(s) Administered**

The study intervention(s) to be used in this study are outlined in [Table 2](#).

Each assigned study interventions will be administered orally once daily. As there is no recommended dosing time, the participant should take their treatment at a consistent time each day and participants are suggested to avoid taking the study intervention with other concomitant medications at the same time. On the visit day, the participant should take the medication after all procedures are completed.

Table 2 Study Interventions

During active run-in period:

Cohort Name	Cohort Type	Intervention Name	Type	Dose Formulation	Unit Dose Strength(s)	Dosage Level(s)	Route of Administration	Regimen/ Treatment Period	Use	IMP/N IMP	Sourcing
A	Active Comparator	atorvastatin	Drug	Tablet	10 mg	10 mg QD	Oral	Run-in period/ 5 weeks	Active treatment to select uncontrolled participants	NIMP	Provided centrally by the Sponsor
B	Active Comparator	atorvastatin	Drug	Tablet	20 mg	20 mg QD	Oral	Run-in period/ 5 weeks	Active treatment to select uncontrolled participants	NIMP	Provided centrally by the Sponsor
Definition Investigational Medicinal Product (IMP) and Non-Investigational Medicinal Product (NIMP) is based on guidance issued by the European Commission. Regional and/or Country differences of the definition of IMP/NIMP may exist. In these circumstances, local legislation is followed.											

During double-blinded treatment period:

Arm Name	Arm Type	Intervention Name	Type	Dose Formulation	Unit Dose Strength(s)	Dosage Level(s)	Route of Administration	Regimen/ Treatment Period	Use	IMP/ NIMP	Sourcing
A1	Experimental	MK-0653C FDC (ezetimibe 10 mg + atorvastatin 10 mg)	Drug	Tablet	10 mg / 10 mg	10 mg / 10 mg QD	Oral	Randomization treatment: 12 weeks	Experimental	IMP	Provided centrally by the Sponsor
	Placebo	Placebo atorvastatin	Drug	Tablet	0 mg	0 mg QD	Oral	Randomization treatment: 12 weeks	Dummy with study treatment	NIMP	Provided centrally by the Sponsor
A2	Active Comparator	atorvastatin	Drug	Tablet	20 mg	20 mg QD	Oral	Randomization treatment: 12 weeks	Active control	NIMP	Provided centrally by the Sponsor
	Placebo	Placebo of MK-0653C FDC (ezetimibe 10 mg + atorvastatin 10 mg)	Drug	Tablet	0 mg	0 mg QD	Oral	Randomization treatment: 12 weeks	Dummy with study treatment	NIMP	Provided centrally by the Sponsor

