### **8.11.2 Run-In (Visit 2 and Visit 3)**

Visit 2 will be performed approximately 5 weeks prior to randomization (Visit 4).

Dispense run-in intervention to a participant if he/she is eligible for study participation. Participants will be instructed to take 1 tablet from the bottle.

After initiating administration, participant who is determined to be not appropriate by the investigator will be excluded the study as screen failed. If a participant is not eligible for study participation, the investigator should contact with the participant, stop dosing study drug and performing the end of study visit immediately, and a safety follow-up visit by phone-call as appropriate.

*NOTE: it is not necessary for screen failed participant who did not start the study intervention to perform follow-up visit after the end of study visit.*

Approximately 4 weeks after Visit 2, participants will be scheduled to return for Visit 3. Blood lipid levels (e.g. LDL-C values) and biochemistry test measured at Visit 3 (Week -1) will be used to determine participant's eligibility for intervention allocation/randomization at Visit 4 (Day 1/Week 0).

Participant will be instructed on Chinese Guidelines on Prevention and Treatment of Dyslipidemia in Adults (2016 Edition), and will agree to maintain the diet/exercise regimen throughout the study.

No rescreening will be allowed of participants who discontinue during the run-in phase or fail to be eligible after the run-in phase.

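### The SoA schedules neither a pregnancy test nor an eligibility check at Visit 2, where run-in atorvastatin starts and the participant must still not be pregnant

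*Combined protocol and SAP*

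**What the plan says.** Section 5.1 states that inclusion criteria 1 to 8 are to be met at Visit 1 and at Visit 2. Criterion 6 is in that block and includes not being pregnant. Section 8.11.2 makes dispensing of run-in drug conditional on the participant being eligible.

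Criterion 17, listed among the Visit 1 exclusions in Section 5.2, concerns "A WOCBP who has a positive urine pregnancy test within 24 hours before the first dose of study intervention". Section 10.5.3 sets out three steps for WOCBP: a negative test for inclusion, a repeat no more than 24 hours before the first dose, and tests at scheduled visits during the treatment period.

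The SoA (Section 1.3) has three relevant rows:

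- "Run-in atorvastatin administration/dispensing" is marked at Visit 2 only.
- "Inclusion/Exclusion Criteria" is marked at Visits 1 and 4.
- The pregnancy test row, "Urine/ Serum β-Human Chorionic Gonadotropin (β-hCG; WOCBP only", is marked at Visits 1, 4, 5 and 6.

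**The concern.** Visit 2 is the point at which the trial first gives a drug. Participants stop their own statin before it (Section 4.1) and receive atorvastatin supplied by the sponsor. The criteria require a WOCBP not to be pregnant at that point, but a site working from the SoA is prompted neither to test nor to go back over eligibility. A pregnancy that was too early to detect at Visit 1, or that began between Visits 1 and 2, meets no scheduled test until Visit 4.

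What is at stake is avoidable exposure to run-in drug in early pregnancy, and sites differing in how they apply the 24-hour rule. The primary analysis is not at stake.

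**Working it through.** The plan gives no figure of its own here, so the check compares the SoA rows and the text, then counts days.

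**1. The SoA columns.** Vital signs are included to show that the Visit 2 column is populated elsewhere, so the blanks are not shifted cells.

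| Row | V1 | V2 | V3 | V4 | V5 | V6 |
|---|---|---|---|---|---|---|
| Eligibility criteria | X | – | – | X | – | – |
| β-hCG | X | – | – | X | X | X |
| Run-in dispensing | – | X | – | – | – | – |
| Vital signs | X | X | X | X | X | X |

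**2. Which first dose does the 24-hour rule cover?**

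*Broad reading: the first run-in dose.* Section 6 says "Study intervention is defined as any investigational intervention(s), marketed product(s), placebo, or medical device(s) intended to be administered to a study participant". Section 6.1 adds that "The study intervention(s) to be used in this study are outlined in" Table 2, and Table 2 opens with run-in atorvastatin, whose use is given as "Active treatment to select uncontrolled participants". The note in Section 8.11.2 on run-in screen failures uses the term in the same way: "it is not necessary for screen failed participant who did not start the study intervention to perform follow-up visit". Appendix 3 also names run-in intervention, but only for defining adverse events, so it is not relied on. On this reading the SoA lacks the 24-hour test at Visit 2.

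*Narrow reading: the first randomized dose.* The Table 2 footnote puts the first dose of trial treatment at Visit 4. The three steps of Section 10.5.3 match Visits 1, 4 and 5–6. Section 7.1 keeps participants who stop study intervention in the trial, whereas Section 5.5 makes those who stop during run-in failures, so in Section 7.1 the term must mean randomized drug. Exclusion 31 plausibly carries criterion 17 forward to Visit 4. On this reading the SoA satisfies the rule.

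Inclusion 6 applies at Visit 2 under both readings.

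**3. Age of the test at the first run-in dose.** Inputs: Visit 1 at Week −7 or −6; Visit 2 at Week −5 ± 7 days (SoA); screening of up to 2 weeks (Section 8.11.1).

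- Nominal: (−5 − (−6)) × 7 = 7 days; (−5 − (−7)) × 7 = 14 days.
- With the window: minimum 7 − 7 = 0; maximum 14 + 7 = 21, capped at 14 by the screening limit. Range 0–14 days.

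**4. Time to the next scheduled test.** Visit 4 is dated from Visit 2: 5 × 7 = 35 days; with ± 3 days, 32–38.

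**5. Spacing between scheduled tests.**

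- Visit 1 to Visit 4: nominally 42–49 days; with windows 0 + 32 = 32 to 14 + 38 = 52.
- Visit 4 to Visit 5: 42 ± 7 = 35–49 days.
- Visit 5 to Visit 6: both are dated from Visit 4, at days 35–49 and 77–91, so the longest gap is 91 − 35 = 56 days.

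A Visit 2 test cuts the longest gap before randomization from 52 to 38 days. The longest gap in the whole trial stays at 56. Scheduled tests per WOCBP rise from 4 to 5.

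**6. Rough bound on pregnancies begun between Visits 1 and 2.** Appendix 5 gives the allowed methods a failure rate below 1% per year. Assuming correct use from consent and a constant rate, 1% × 14/365 = 0.038%, so under 0.04% per WOCBP. This does not count conceptions before consent.

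**The case against.** The strongest reply is that requiring a condition to hold is not requiring it to be retested. Inclusion 1 (hypercholesterolemia) must also hold at Visit 2, and no lipid panel is scheduled there, so relying on Visit 1 results is the general design. The eligibility check also exists in the text: Section 5.1 names Visit 2, Section 8.1.2 requires the investigator to review all criteria, Section 8 requires screening evaluations to be reviewed, and Section 8.11.2 ties dispensing to eligibility. These points stand. They reduce the missing eligibility mark to a gap between schedule and text. They do not say how absence of pregnancy is to be confirmed at Visit 2.

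The safety argument is also limited. Participants have been on a stable statin for at least 4 weeks before Visit 1, WOCBP follow contraceptive guidance from consent, a missed cycle already requires a test (Section 10.5.3), and Appendix 2 allows unscheduled tests. A pregnancy begun after Visit 1 is at most 14 days old at Visit 2 and may still be undetectable. All of this stands. What a Visit 2 test mainly adds is detection of pregnancies that were too early to show at Visit 1.

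A reader might infer three stronger things that the documents do not support:

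- *The SoA plainly breaches the 24-hour rule.* It does so only on the broad reading; the narrow one is equally plausible.
- *Five weeks on run-in drug without a test is out of line.* The 32–38 days is no longer than the 35–49 days accepted between Visits 4 and 5. The gap is the missing test before run-in, not the spacing after it.
- *The pregnancy stopping rule in Section 7.1 governs run-in.* That rule is written for participants who go on being monitored, not for run-in failures.

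**Conclusion.** There is a small but real mismatch at run-in entry. Non-pregnancy must hold and eligibility must be established at Visit 2, and the SoA schedules nothing to verify either. At the first run-in dose the last scheduled test is nominally 7–14 days old (0–14 with the window and the screening limit). On the broad reading this compares with a 24-hour maximum. On the narrow reading no time limit applies at Visit 2 and only the verification gap remains.

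The day counts assume that visits keep to the SoA windows and that Section 8.11.1 caps screening at two weeks. The documents do not give the number of WOCBP, so expected cases cannot be estimated. The benefit of a change is modest, and sample size, type I error and power do not depend on it. It is worth making because it costs very little and removes an ambiguity that sites would otherwise resolve for themselves.

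**What to change.** In the Visit 2 column of the SoA, mark urine β-hCG (WOCBP only) and the eligibility criteria, both to be completed before run-in drug is dispensed. Keep the Visit 4 test. In criterion 17 and Section 10.5.3, state whether the 24-hour rule covers the first run-in dose, the first randomized dose, or both. If the sponsor intends only the randomized dose, say so; the Visit 2 marks remain useful because inclusion 6 applies there.

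The cost is one extra site urine test per WOCBP at a visit that already takes place, two SoA cells, and one phrase in each of two sections. If the sponsor has meant the randomized dose all along, extending the rule to run-in would be a new requirement rather than a clarification, and should be presented that way.

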### **Prior/Concomitant Therapy**

18. Participant is currently taking medications that are potent modulators of cytochrome P-450 3A4 (CYP3A4) including:

- Cyclosporine
- Systemically administered azole antifungals such as ketoconazole, fluconazole, and itraconazole
- Macrolide antibiotics (e.g., clarithromycin, and erythromycin)
- Protease inhibitors (e.g., ritonavir, saquinavir, and lopinavir)
- Grapefruit or juice of grapefruit (200 ml/day for more than 3 times per week).

19. Participant is taking any cyclical hormones (e.g., cyclical oral contraceptives, cyclical hormone replacement), including the combination of ethinyl estradiol and norethisterone, or non-cyclical hormones, including non-cyclical hormone replacement therapy (HRT) or any estrogen antagonist/agonist within 8 weeks.

Note: If participant has been treated with a stable regimen of non-cyclical HRT for > 8 weeks and agree to continue this regimen for the duration of the trial, concomitant therapy is acceptable.

20. Participant is receiving treatment with systemic corticosteroids (intravenous, intramuscular and oral steroids).

21. Participant is treated with psyllium, other fiber-based laxatives, phytosterol margarine, and herbal medicine and/or over the counter (OTC) therapies that are known to affect serum lipids.

Note: If participant has been treated with a stable regimen for > 8 weeks and agree to continue this regimen for the duration of the trial, concomitant therapy is acceptable.

22. Participant is treated with an anti-obesity drug (e.g. mazindol) within 12 weeks prior to Visit 1.

23. Participant is treated with warfarin or warfarin-like anticoagulants and has not been on a stable dose with a stable International Normalized Ratio (INR) for at least 6 weeks.

24. Participant has taken lipid-lowering agents (except probucol) including, Cholestin™, bile acid sequestrants, ezetimibe, fibrates or niacin (>200 mg/day), PCSK9 inhibitors within 6 weeks prior to Visit 1. Participant has taken probucol within 10 weeks prior to Visit 1.

### **Prior/Concurrent Clinical Study Experience**

25. Participant who has been treated with any other investigational drug within 30 days of Visit 1.

### **Diagnostic Assessments**

Not applicable.

### **Other Exclusions**

26. Participant who currently follows an excessive weight reduction diet in the opinion of the investigator.

27. Participant currently engages in a vigorous exercise regimen (e.g.; marathon training, body building training) or intends to starts training during the trial.

28. Is or has an immediate family member (eg, spouse, parent/legal guardian, sibling, or child) who is investigational site or Sponsor staff directly involved with this study.

### **Visit 4 Criteria**

29. Participant reaches the treatment goal with mono-statin therapy [per central lab].

30. Participant has creatine kinase (CK) levels > 3 X ULN [per central laboratory reference ranges].

31. Participant has developed a new medical condition, suffered a change in status of an established medical condition or required a new treatment or medication, which meets any, previously described trial exclusion criteria.

### **5.3 Lifestyle Considerations**

#### **5.3.1 Meals and Dietary Restrictions**

Participants should be instructed for diet or a similar diet according to China 2016 Guideline at Visit 1. Participants also should keep exclusion criteria 24 (Participant consumes less than 0.2 L of grape fruit juice per day.) during trial period.

At each subsequent trial visit, the dietary compliance will be monitored and sites should reinstruct participants who are not compliant. This monitoring is particularly important in an effort to minimize any diet-related lipid changes.

Participants should fast (no food or drink except water) for at least 10 hours prior to all scheduled trial visits. Permitted concomitant therapies can be taken during the fasting period.

Note: If the participant reports to the visit without having fasted, the sample should not be drawn, and the participant should be asked to return for another appointment.

### 5.3.2 Caffeine, Alcohol, and Tobacco Restrictions

Participants will be suggested not consume more than the 25 g alcohol per day.

Participants will not be permitted in the trial if they consistently consume excessive amounts of alcohol. Participants should be encouraged not to make major changes in their alcohol consumption for the duration of the trial. Please refer to [Table 1](#) for reference volume of alcohol.

Table 1 Alcohol Consumption Quantities

Alcohol	25 g/day
Beer	1 bottle (633 ml/bottle)
Sake	180 ml
Whiskey/ Brandy	2.5 glasses (single)
Distilled spirit	90 ml
Wine	2 glasses

Participants should refrain from smoking during the trial.

### 5.3.3 Activity Restrictions

Participants should continue any activity he/she was accustomed to prior to entering the trial, but should refrain from engaging in a vigorous exercise regimen during the trial. Participants should be instructed the activity by investigator based on Chinese Guidelines on Prevention and Treatment of Dyslipidemia in Adults. Participant also should keep Exclusion Criterion 27 and 28 (Participant does not follow excessive weight reduction diet from trial duration, and does not engage in a vigorous exercise regimen or start training) during the trial.

